#### AEs of Special Interest

AEs of special interest are defined in Table 3.

Table 3Selection Criteria for AEs of Special Interest

Event of special interest	
Convulsions (seizure)	Narrow SMQ of 'Convulsions'
Hypertension	Narrow SMQ of 'Hypertension'
Neutrophil count decreased	Preferred terms of 'Neutrophil count decreased', 'Neutropenia', 'Agranulocytosis',' Granulocyte count decreased', 'Granulocytopenia', 'Febrile neutropenia', 'Neutrophil percentage decreased', 'Band neutrophil count decreased', and 'Band neutrophil percentage decreased' 'Neutropenic sepsis', 'Neutropenic infection', 'Neutrophil count characteresed'
Cognitive and memory	All preferred terms in MedDRA HI GT 'Mental impairment disorders'
impairment	An preferred terms in MedDKA TILOT Mental impairment disorders
Ischemic Heart Disease (IHD)	Narrow SMQs of 'Myocardial Infarction' and 'Other ischemic heart disease'
Other selected cardiovascular events	Narrow SMQs of 'Haemorrhagic central nervous system vascular conditions,' 'Ischaemic central nervous system vascular conditions' and 'Cardiac failure'
Posterior reversible encephalopathy syndrome (PRES)	Preferred term 'Posterior reversible encephalopathy syndrome'
Fatigue	Preferred terms of 'Fatigue', 'Asthenia'
Renal disorder	Broad SMQ of 'Acute Renal Failure'
Second primary malignancies	Narrow SMQs of 'Malignant or unspecified tumours' customized to exclude preferred terms of 'Congenital fibrosarcoma', 'Congenital malignant neoplasm', 'Congenital retinoblastoma', ', "Metastases to", 'Metastasis', 'Metastatic neoplasm', 'Prostate cancer', 'Carcinoid tumour of the prostate', 'neoplasm prostate' AND (inclusive of) Narrow SMQ of 'Myelodysplastic syndrome' AND (inclusive of) All preferred terms under HLT of 'Myeloproliferative disorders (excl. leukaemias)'
Table continued on next page	Note: Non-melanoma skin cancers are excluded (preferred terms of 'Basal cell carcinoma', 'Basosquamous carcinoma', 'Basosquamous carcinoma of skin', 'Keratoacanthoma', 'Skin cancer', 'Skin cancer metastatic', 'Squamous cell carcinoma', 'Squamous cell carcinoma of skin', 'Lip squamous cell carcinoma')
- and the second of the puge	

Event of special interest				
Fall	Preferred term of 'Fall'			
Fracture	All preferred terms under the MedDRA HLGT of 'Fractures', 'Bone and			
	joint injuries'			
Loss of consciousness	Preferred terms of 'Loss of consciousness', 'Syncope',' Presyncope'			
Thrombocytopenia	Preferred terms of 'Thrombocytopenia', 'Platelet count decreased'			
Musculoskeletal events	Preferred terms of 'Back pain', 'Arthralgia', 'Myalgia', 'Musculoskeletal			
	pain', 'Pain in extremity', 'Musculoskeletal stiffness', 'Muscular			
	weakness', 'Muscle spasms'			
Severe cutaneous adverse	Narrow SMQ of 'Severe cutaneous adverse reactions'			
reactions (SCAR)				
Angioedema	Narrow SMQ of 'Angioedema'			
Rash	Preferred terms of 'Butterfly rash', 'Exfoliative rash', 'Eyelid rash',			
	'Genital rash', 'Heliotrope rash', 'Mucocutaneous rash', 'Nodular rash',			
	'Paraneoplastic rash', 'Penile rash', 'Perineal rash', 'Rash', 'Rash			
	erythematous', 'Rash follicular', 'Rash macular', 'Rash maculo-papular',			
	'Rash maculovesicular', 'Rash morbilliform', 'Rash neonatal', 'Rash			
	papular', 'Rash papulosquamous', 'Rash pruritic', 'Rash pustular', 'Rash			
	rubelliform', 'Rash scarlatiniform', 'Rash vesicular', 'Septic rash',			
	'Systemic lupus erythematosus rash', 'Vasculitic rash', 'Viral rash',			
	'Vulvovaginal rash'			
Hepatic disorder	Narrow SMQs of 'hepatic failure, fibrosis and cirrhosis and other liver			
	damage related conditions', 'hepatitis, non-infectious' and 'liver related			
	investigations, signs and symptoms'			

An overview table of the TEAEs of special interest will be described by the number and percentage of patients with TEAEs of special interest per treatment group and overall.

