In a 6-month study in transgenic rasH2 mice, enzalutamide did not show carcinogenic potential (absence of neoplastic findings) at doses up to 20 mg/kg per day (AUC24h ≈317 μg·h/mL), which resulted in plasma exposure levels similar to the clinical exposure (AUC24h 322 μg·h/mL) in metastatic CRPC patients receiving 160 mg, daily. Daily oral dosing of rats with enzalutamide at 10 to 100 mg/kg for 2 years increased the incidence of neoplastic findings (compared to control) that were considered related to the primary pharmacology of enzalutamide. These included benign thymoma, fibroadenoma in the mammary glands and benign Leydig cell tumors in the testes in males; benign granulosa cell tumor in the ovaries in females; and adenoma in the pars distalis of the pituitary in both sexes. In addition, urothelial papilloma and carcinoma of urinary bladder in male rats were observed at the 100 mg/kg per day dose and were considered secondary to the irritation caused by the increased urinary crystal/calculi, which is known to occur in rodent species. Leydig cell tumors in rats are generally not considered relevant to humans based on experience with other anti-androgens. The human relevance of thymoma, pituitary adenoma and fibroadenoma in rats is unclear, but a potential relevance cannot be ruled out. The exposure levels (based on AUC) achieved in this study for enzalutamide and its metabolites (M1 and M2) in rats were less than or similar to those in prostate cancer patients at the recommended dose of enzalutamide (Section 5.3, Company Core Data Sheet version 6.0).

Enzalutamide was nonmutagenic in bacteria, nonclastogenic in mammalian cells and nongenotoxic in vivo in mice. The 2 major human metabolites (*N*-desmethyl enzalutamide and an inactive carboxylic acid derivative) were negative for mutagenicity in the bacterial reverse mutation assay (refer to the current Investigator's Brochure).

- CONFIDENTIAL -

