# 5.5 Adverse Events and Other Safety Aspects

### **5.5.1** Definition of Adverse Events

An AE is defined as any untoward medical occurrence in a subject administered a study drug or has undergone study procedures and which does not necessarily have a causal relationship with this treatment. An AE can therefore be any unintended sign (including an abnormal laboratory finding), symptom, or disease temporally associated with the use of a medicinal (investigational) product, whether or not related to the medicinal (investigational) product.

Some countries may have additional local requirements for events that are required to be reported as AEs or in an expedited manner similar to a SAE. In these cases, it is the investigator's responsibility to ensure these AEs or other reporting requirements are followed and the information is appropriately recorded in the electronic case report form (eCRF) accordingly.

An abnormality identified during a medical test (e.g., laboratory parameter, vital sign, ECG data, physical examination) should be defined as an AE only if the abnormality meets 1 of the following criteria:

- Induces clinical signs or symptoms;
- Requires active intervention;
- Requires interruption or discontinuation of study medication;
- The abnormality or investigational value is clinically significant in the opinion of the investigator.

Clinical signs or symptoms of disease progression will be recorded as AEs. However, disease progression itself should not be recorded as an AE unless the disease progression results in death; this event is recorded as an AE with 'disease progression' as the reported term.

EudraCT number 2015-003869-28

- CONFIDENTIAL -

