# 12.3 Common Serious Adverse Events

The following is a list of SAEs that the sponsor considers to be associated with the disease state being studied. The list does **NOT** change the investigator's reporting obligations or prevent the need to report an AE meeting the definition of an SAE as detailed in [Section 5.5.2 Definition of Serious Adverse Events]. The purpose of this list is to note that some events reported as SAEs may not require expedited reporting to the regulatory authorities based on the classification of "common SAEs." The investigator is required to follow the requirements detailed in [Section 5.5.5 Reporting of Serious Adverse Events].

For IND safety reporting, single occurrences of the following events may be excluded from expedited reporting to the FDA. If aggregate analysis of these events indicates they occur more frequently with study drug, an expedited IND safety report may be submitted to the FDA.

- Anemia
- Anorexia
- Asthenia/Fatigue
- Bone pain
- Back pain
- Catheter-related infection
- Dyspnea
- Hematuria
- Hydronephrosis
- Metastases to bone
- Metastases to central nervous system
- Nausea
- Obstructive uropathy
- Pain
- Prostate cancer metastatic
- Renal failure
- Renal failure acute
- Spinal compression fracture
- Spinal cord compression
- Urinary retention
- Urinary tract infection
- Urinary tract obstruction
- Vomiting

Sponsor: APGD EudraCT number 2015-003869-28

- CONFIDENTIAL -

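### The second-primary-malignancy definition in SAP Table 3 does not name 'Prostate cancer metastatic' as excluded, so a report coded to that term could be counted as a second cancer

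*SAP*

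**What the plan says.** The second-primary row of SAP Table 3 starts from "Narrow SMQs of 'Malignant or unspecified tumours' customized to exclude preferred terms of 'Congenital fibrosarcoma" and continues with further exclusions, ending with "Metastasis', 'Metastatic neoplasm', 'Prostate cancer', 'Carcinoid tumour of the prostate', 'neoplasm prostate' AND". A 'Metastases to' entry also stands in the list. The row then adds the myelodysplastic and myeloproliferative terms and, in a note, removes non-melanoma skin cancers. That note includes the run "Skin cancer', 'Skin cancer metastatic', 'Squamous cell carcinoma".

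Protocol Appendix 12.3 introduces its common events this way: "The following is a list of SAEs that the sponsor considers to be associated with the disease state being studied". Three entries in it concern metastatic cancer: 'Metastases to bone', 'Metastases to central nervous system' and "Prostate cancer metastatic".

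On recording progression, protocol 5.5.1 says that "disease progression itself should not be recorded as an AE unless the disease progression results in death". A fatal case is then entered with 'disease progression' as the reported term.

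SAP 7.5.1 reports events of special interest as the number and percentage of patients by treatment group. No test is attached.

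**The concern.** The exclusions are evidently meant to keep the cancer under study, and its spread, out of a category for new cancers. One term that the sponsor itself expects to see reported in this disease is not written there. Inclusion criterion 4 (protocol 3.2) requires documented metastatic prostate cancer, so a report of metastatic prostate cancer in this trial describes the index disease.

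At stake is the accuracy of one safety category. Exclusion criterion 10 (protocol 3.3) bars most recent other invasive cancers, so true second primaries are probably few, and a handful of misclassified reports could change the comparison between groups. Protocol 1.2.1 says of some tumours seen in the two-year rat study that "a potential relevance cannot be ruled out". That is modest support, since it refers to thymoma, pituitary adenoma and fibroadenoma, and the thymoma is described as benign.

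**Working it through.** The plan states no figure to reproduce, so the check sets the two lists side by side and asks what must be true for a miscount.

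**1. Term by term.** Metastatic-cancer entries in Appendix 12.3 against the Table 3 exclusions:

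| Appendix 12.3 entry | Removed by Table 3? |
|---|---|
| 'Metastases to bone' | Yes, through 'Metastases to' |
| 'Metastases to central nervous system' | Yes, through 'Metastases to' |
| 'Prostate cancer metastatic' | Only if 'Prostate cancer' is read as a stem |

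Two of the three are removed on any reading and one is not.

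**2. Exact term or stem?** 'Metastases to' names no site, so it can only work as a stem. The other entries look like full terms. The same row writes out 'Skin cancer' and 'Skin cancer metastatic', 'Squamous cell carcinoma' and 'Squamous cell carcinoma of skin', and 'Basosquamous carcinoma' and 'Basosquamous carcinoma of skin'. The Rash row likewise gives 'Rash' and then its variants. Under stem matching the second member of each pair would be redundant. Exact matching is therefore the better reading, but the SAP does not state it.

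**3. Is the term in the query?** The SAP names MedDRA v23.0 but does not reproduce the query's content. Membership is inferred: 'Prostate cancer' had to be subtracted, and so did 'Skin cancer metastatic', which suggests that the query carries metastatic forms of named cancers.

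**4. Can such a report arise?** Section 5.5.1 should keep most progression out of the AE data. Table 3 nevertheless removes 'Prostate cancer' and several metastasis terms, which would hardly be needed if sites never reported index-cancer events. Protocol 5.5.7 and Appendix 12.3 also keep the duty to report the listed serious events.

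**5. Size and direction.** The documents give no rates, so the following is assumed throughout. Take true second primaries of 3% on enzalutamide and 2% on placebo (ratio 3/2 = 1.50), and suppose that no subject has both kinds of event.

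| Assumed misclassified reports, enzalutamide v placebo | Resulting percentages | Ratio |
|---|---|---|
| 0.5% v 1% | 3.5% v 3% | 1.17 |
| 1% v 2% | 4% v 4% | 1.00 |
| 1% v 3% | 4% v 5% | 0.80 |
| 1% v 0.5% (first row reversed) | 4% v 2.5% | 1.60 |
| 2% v 1% (second row reversed) | 5% v 3% | 1.67 |
| 3% v 1% (third row reversed) | 6% v 3% | 2.00 |

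A few reports can move the ratio materially, but its direction follows entirely from the assumed split between groups.

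**The case against.** The strongest reply is that several links are unproven.

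- Query membership is not shown. This stands as a stated assumption.
- 'Prostate cancer' might be meant as a stem, as 'Metastases to' must be, and a stray empty item just before 'Metastases to' could mean that an entry was lost. The paired entries favour exact terms without settling the matter, so the SAP should say which it is.
- Section 5.5.1 keeps non-fatal progression out of the AE data and gives fatal progression another reported term. This stands as a limit on frequency. A reader might infer that progression of the index cancer is routinely counted as a second cancer. The documents do not support that: only reports made despite the rule, or otherwise coded to this term, are exposed.
- Appendix 12.3 serves expedited-reporting purposes, and an entry such as 'Asthenia/Fatigue' shows that it is not a strict preferred-term list. That is fair, but it still shows that the sponsor anticipates such reports.
- Any such event would also appear on its own line in the preferred-term tables, in the rates per 100 patient-years and in the listings. This makes a miscount discoverable but does not correct the category.
- Second primary malignancy is not among the special-interest events in protocol 1.3 or the four important identified risks in protocol 1.4. That lowers the stakes. The SAP nevertheless chose to track it.

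A reader might also infer that errors would fall mainly on placebo and so hide an excess on enzalutamide, because progression is likelier there. The documents do not establish this. Under SAP 6.3 the Enzalutamide window spans double-blind and open-label treatment, while the Placebo window is cut at the start of open-label enzalutamide. The overview uses plain percentages of patients, so longer observation could push the count the other way.

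**Conclusion.** The point holds in a limited form. As written, and on the better reading of the table, the definition fails to exclude a term that the protocol expects and that cannot denote a second primary in this population. A treatment-emergent event coded to it would be counted wrongly if two assumptions hold: entries are matched as exact terms, and the term is inside the query. The effect is nil if either fails or if no such event is coded.

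Neither the size nor the direction of any distortion between groups can be derived from the documents, and the scenarios above are illustrations only. The consequence is confined to a descriptive safety table. No hypothesis test, error rate or efficacy conclusion is touched. The correction is still worth making, because it concerns the content of a safety count and the omitted term is specific.

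**What to change.** In SAP Table 3, add 'Prostate cancer metastatic' to the exclusions for second primary malignancies, together with any other term in the query that denotes the index prostate cancer, identified by checking the query content in the MedDRA version used. State for each entry whether it is an exact preferred term or a stem, and resolve the empty item before 'Metastases to'. Apply the same list to the Enzalutamide, Placebo and Placebo crossover groups.

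The cost is a check of the query and a few programmed terms. No new data are needed. Excluding 'Prostate cancer metastatic' removes no true second primary, since every subject enters with that disease.

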When adjusted for treatment duration, the event rates for grade  $\geq$  3 TEAEs showed small differences ( $\leq$  1.2 events per 100 patient years) between the enzalutamide group and the placebo group.

Study drug-related TEAEs reported in  $\geq$  5% of patients in the enzalutamide group were fatigue (24.1% enzalutamide vs 14.1% placebo), hot flush (14.0% vs 8.7%), nausea (11.7% vs 10.4%), decreased appetite (8.2% vs 5.5%), asthenia (7.4% vs 4.4%), diarrhea (5.6% vs 4.4%) and hypertension (5.6% vs 2.0%).

The incidence of TEAEs leading to death was low in the pooled enzalutamide groups (4.8%) and in the placebo group (2.8%) and the adjusted event rates for serious TEAEs were also comparable in both groups.

The incidence of TEAEs leading to permanent discontinuation of study drug was similar in both groups; 17.2% in the pooled enzalutamide groups and 16.1% in the placebo group. The incidence of TEAEs leading to a dose reduction was 5.6% in the phase 3 enzalutamide group and 2.0% in the phase 3 placebo group. The incidence of TEAEs leading to a dosing interruption was 15.0% in the phase 3 enzalutamide group and 9.9% in the phase 3 placebo group

The pooled phase 3 safety data confirms that convulsion/seizure, cognitive and memory impairment, fatigue-related events, neutropenia/neutrophil count decreased, fall, fracture and hypertension are adverse events of special interest (AESI) for enzalutamide. Posterior reversible encephalopathy syndrome (PRES) is also considered an AESI for enzalutamide; however, this is based on cases reported during postapproval use of enzalutamide and not on events occurring in clinical studies.

Severe cutaneous adverse reactions, including acute generalized exanthematous pustulosis, dermatitis bullous, dermatitis exfoliative generalized, drug reaction with eosinophilia and systemic symptoms, erythema multiforme, exfoliative rash, Stevens-Johnson syndrome, toxic epidermal necrolysis and toxic skin eruption have been reported in post-marketing cases.

For more information on the investigational product enzalutamide and on the clinical study experience, refer to the current Investigator's Brochure of enzalutamide.

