Lastly, the primary efficacy analysis in ARCHES demonstrated a statistically significant, robust and substantial improvement in radiographic progression-free survival together with clinically meaningful improvements in the key secondary endpoints of time to PSA progression, time to start of a new antineoplastic therapy, PSA undetectable rate and objective response rate and a trend in OS (observed at the time of interim analysis) in favor of enzalutamide plus ADT versus placebo plus ADT treatment. For the secondary endpoints, the ARCHES study demonstrated that enzalutamide prolonged the time to the first symptomatic skeletal event and time to castration-resistance. Assessments of patient-reported outcomes data showed that patients receiving enzalutamide plus ADT in ARCHES had a high baseline level of quality of life, which was maintained over time.

Based on the safety information collected to date in clinical trials and in commercial use, the safety profile experienced by patients remains consistent with the approved product label as well as events that can be seen in patients with prostate cancer. The safety profile in mHSPC patients in this study is expected to be consistent with the established safety profile for enzalutamide. To date, there are 4 important identified risks associated with enzalutamide (seizure, fall, nonpathological fracture and ischemic heart disease). While serious adverse events (SAEs) such as seizure have occurred in patients receiving treatment with enzalutamide, these events have been rare. To mitigate the risk of seizure, subjects with a history of seizure or any condition that may predispose to seizure (e.g., prior cortical stroke or significant brain trauma, brain arteriovenous malformation) are excluded from the trial. Study drug discontinuation is required for subjects experiencing either seizure or PRES. In addition to these patient exclusion and discontinuation requirements, the study design includes safety labs, scans and guidance related to concomitant medications to minimize the risks associated with enzalutamide and ensure timely intervention if needed.

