### Time to first SSE:

Time to first SSE is defined as the time from randomization to the occurrence of the first SSE. SSE is defined as radiation or surgery to bone, clinically apparent pathological bone fracture or spinal cord compression. The analysis method will be the same as for rPFS.

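### The pooled Fracture row in SAP Table 3 does not isolate nonpathological fracture, the risk the protocol names, and can dilute or mask a difference in it; a second row would report it

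*SAP*

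**What the plan says.** SAP 7.5.1, Table 3, fills the Fracture row with "All preferred terms under the MedDRA HLGT of 'Fractures', 'Bone and" joint injuries. The row excludes nothing and does not separate fractures by cause. The overview table then gives, for each event of special interest, the count and percentage of patients by treatment group.

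The protocol describes the risk in two places, with different words:

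- Section 1.3, on events of special interest: "neutropenia/neutrophil count decreased, fall, fracture and hypertension are adverse events of special interest (AESI) for enzalutamide". Here fracture is unqualified.
- Section 1.4, on important identified risks: "there are 4 important identified risks associated with enzalutamide (seizure, fall, nonpathological fracture and ischemic heart disease". Here it is nonpathological fracture only.

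Three other passages bear on disease-related fracture. Protocol 7.4.2 makes pathological fracture part of an efficacy endpoint: "SSE is defined as radiation or surgery to bone, clinically apparent pathological bone fracture or spinal cord compression". Protocol 5.5.1 states: "Clinical signs or symptoms of disease progression will be recorded as AEs". Appendix 12.3, the sponsor's list of serious events associated with the disease, includes "Spinal compression fracture".

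**The concern.** All subjects have metastatic disease, so fractures can come from the cancer or from other causes. The identified risk in Protocol 1.4 is the second kind. The first kind is something effective treatment may reduce: Protocol 1.4 reports that enzalutamide prolonged time to first symptomatic skeletal event in this trial. If one row counts both kinds, an excess of nonpathological fracture on enzalutamide could be partly offset by fewer pathological fractures. Non-fracture bone or joint injuries, if the second group contains them as its title suggests, would dilute the ratio further.

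What is at stake is how clearly the safety tables show one of four named risks. The OS test, its significance level and its power are not affected.

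**Working it through.** **Is there a figure to reproduce?** No. The documents give no fracture rate and no power or precision statement for this event. The check is a reading of the text plus an illustration in which every rate is assumed.

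**Step 1. Can disease-related fractures reach the row?** Yes in principle. Protocol 5.5.1 records signs of progression as adverse events, and Appendix 12.3 treats one fracture term as disease-associated. Protocol 5.1.3.4 allows palliative radiation and palliative surgery for skeletal events without stopping study drug, so a patient with such an event can stay inside the treatment-emergent period of SAP 6.3.

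**Step 2. Does another planned output give the missing count?** Not fully. SAP 7.5.1 tabulates all treatment-emergent events by system organ class and preferred term. One patient can appear under several terms, so those rows cannot be summed to a number of patients with nonpathological fracture. Rates per 100 patient-years are specified by class and term, not by event of special interest.

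**Step 3. How much could pooling matter?** Inputs: 550 per arm (Protocol 7.1); assumed rates for nonpathological fracture (N), pathological fracture (P) and non-fracture injury (J), treated as independent within a patient.

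- Pooled rate in an arm = 1 − (1 − N)(1 − P)(1 − J)
- 95% CI for the difference = (e − p) ± 1.96 × √[e(1 − e)/550 + p(1 − p)/550], with e the enzalutamide and p the placebo rate

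Worked example with N = 8% v 4%, P = 1% v 2%, J = 0: enzalutamide 1 − 0.92 × 0.99 = 8.92%; placebo 1 − 0.96 × 0.98 = 5.92%; ratio 8.92/5.92 = 1.51; difference 3.00 points.

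| N (enza v placebo) | P | J | Pooled | Ratio | Difference, points (95% CI) |
|---|---|---|---|---|---|
| 8% v 4% | none | none | 8.00% v 4.00% | 2.00 | 4.00 (1.20 to 6.80) |
| 8% v 4% | 0.5% v 1% | none | 8.46% v 4.96% | 1.71 | 3.50 (0.55 to 6.45) |
| 8% v 4% | 1% v 2% | none | 8.92% v 5.92% | 1.51 | 3.00 (−0.09 to 6.09) |
| 8% v 4% | 2% v 4% | none | 9.84% v 7.84% | 1.26 | 2.00 (−1.35 to 5.35) |
| 8% v 4% | 3% v 6% | none | 10.76% v 9.76% | 1.10 | 1.00 (−2.59 to 4.59) |
| 8% v 4% | 3% v 3% | none | 10.76% v 6.88% | 1.56 | 3.88 (0.54 to 7.22) |
| 8% v 4% | none | 3% v 3% | 10.76% v 6.88% | 1.56 | 3.88 (0.54 to 7.22) |
| 6% v 3% | 3% v 6% | none | 8.82% v 8.82% | 1.00 | 0.00 (−3.35 to 3.35) |

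Two effects should be kept apart. Events equally common in both arms dilute the ratio but leave the difference almost unchanged (3.88 against 4.00 points). Only events that are less common on enzalutamide shrink the difference, and in the last line they remove it.

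**Step 4. What pushes the other way?** The table reports crude percentages. Under SAP 6.3 the enzalutamide group is observed up to 30 days after its last dose in either period, while the placebo group is also cut off when open-label enzalutamide starts. Longer observation raises the crude percentage on enzalutamide. The period also closes at new antineoplastic therapy, which limits how many fractures after progression are captured at all.

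**The case against.** The case against has several parts.

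- A reader might infer that Table 3 contradicts the protocol. It does not. Table 3 defines events of special interest, and Protocol 1.3 lists that event as plain fracture. This part stands: the gap is between the row and the identified risk in 1.4, not a departure from the list.
- A reader might infer that the row biases the comparison toward no difference and will understate the risk. The documents do not support that. The reported skeletal benefit is for a composite, with no effect given for pathological fracture alone. The preferred terms in the two groups are not listed. Appendix 12.3 calls spinal compression fracture disease-associated, which does not show that it falls with treatment. Exposure may act in the opposite direction. This part also stands.
- The preferred-term tables, the listing of all events and the separate Fall row give partial protection. A pathological-fracture term that was coded as such would be visible. What these outputs lack is a patient-level count of the named risk.
- The second-primary-malignancy row of Table 3 does exclude index-disease terms, but its name requires that. The name Fracture does not. The comparison shows only that tailoring terms is already practised in this table.
- An inclusive definition avoids judging cause. Removing every fracture that a site recorded as a skeletal event would make a safety count depend on site attribution in a study already unblinded, and could delete a drug-related fracture in a metastatic bone. This stands, and it rules out replacing the current row or making that exclusion the main analysis.

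**Conclusion.** The point holds in a limited form. The all-term row is a legitimate summary of fracture as listed in Protocol 1.3, but no planned output gives the number of patients with nonpathological fracture, and the pooled row can dilute or mask a difference in it. Under the assumed rates a true ratio of 2.00 appears as anything from 1.71 down to 1.00 when pathological fractures are halved by treatment. If they do not differ between arms, the ratio is diluted to 1.56 and the difference barely moves.

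These figures rest on assumed rates, on independence within patients, and on pathological-fracture terms lying inside the two groups. The actual size and net direction cannot be determined from the documents. This is a cheap improvement to safety reporting, with no bearing on the efficacy conclusions.

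**What to change.** Leave the current Fracture row of Table 3 as it is. Add a second row for nonpathological fracture, drawn from the same two groups but excluding pathological-fracture preferred terms and non-fracture bone or joint injury terms. Write out the term list before the table is run. Report the row as number and percentage of patients, and per 100 patient-years with the formula already in SAP 7.5.1, so that differing exposure is visible.

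Do not drop a fracture from the safety count merely because the site recorded it as a symptomatic skeletal event. At most, show that exclusion as a labelled sensitivity count, with a stated rule for matching the adverse event to the skeletal event record.

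The cost is a term list and one more row, using data already collected. Some fractures of unclear cause will be misclassified, such as a compression fracture coded without a cause. The retained all-term row covers that.
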